Section 7.2	The following text was added: No additional scans or response assessments are required after the safety follow-up period, however additional scans or response assessments may be performed as part of the patient's standard of care at any time. Deleted "In addition, images from Part B Cohort 2 and Parts C and D will be collected by a blinded independent central review (BICR) facility for possible future analysis." Added "patients should not discontinue treatment" to the following text: When feasible, patients should not discontinue treatment until progression is confirmed.	Update
Section 7.3	The following text was added: Starting with amendment 11, PK and immunogenicity assessments will not be conducted after Cycle 1.	Update
Section 7.4	Replaced "will" with "may" in the following text: Tumor samples and blood for exploratory biomarkers analyses may be collected at protocol-specified time points (see Appendix E). The following text was added: Starting with amendment 11, biomarker assessments will not be conducted after Cycle 1.	Update
Section 7.4.2	Replaced "are collected" with "may be collected" in the following text: To understand dynamic changes of these soluble biomarkers and their relationship to efficacy and safety, blood samples may be collected at various time points during the study.	Clarification
Section 7.4.3	Replaced "will be retained" with "may be retained" in the following text: For patients in the US who provide additional consent, remaining de-identified unused blood and/or tissue may be retained by the sponsor and used for future research, including but not limited to the evaluation of targets for novel therapeutic agents, the biology of ADC sensitivity and resistance mechanisms, and the identification of biomarkers of ADCs.	Clarification

Section(s)	Change	Rationale
Section 7.5.1.2	Added "the completion of the safety follow-up period" to the following text below:	Revision
	Notification to Drug Safety: Complete a Pregnancy Report Form for all pregnancies and lactations that occur from the time of treatment allocation until the completion of the safety follow-up period or 30 days following the last dose of study drug(s) if the patient initiates new anticancer therapy, whichever is earlier.	
Section 7.5.5	Removed the following text "and 24 weeks after EOT (±1 week)" from the following text:	Clarification
	For women of childbearing potential, a serum or urine β-hCG pregnancy test with sensitivity of at least 25 mIU/mL will be performed at baseline, within 3 days prior to each Day 1 study drug dose at each cycle, and at the EOT visit.	
Section 7.6	Replaced "will be performed" with "may be performed" in the following text: Immunogenicity is commonly assessed for biologics; therefore, standard tests may be performed to detect the possible presence of specific antibodies to LV.	Clarification
Section 9.3.2	The following text "the primary analysis will be conducted when all treated patients have been followed for at least 6 months or came off study, whichever comes first" was updated to "the primary analysis will be conducted when all treated patients have come off study."	Update
Appendix A	Concerning footnote B, added "completion of the safety follow-up period" and "unless otherwise stated".	Update
	Concerning footnote F, added "Biomarker assessments will only be collected during Cycle 1 as of protocol amendment 11".	
	Concerning footnote L, added "unless otherwise stated".	
	Concerning footnote T, added "follow-up will occur every 6 weeks (±1 weeks) 30 days post last treatment for patients on LV only and 90 days for those on pembrolizumab."	
	Deleted footnote U, "for Part B Cohort 2, response assessments will be collected by BICR for possible future analysis".	
Appendix B	Concerning footnote C, added "Biomarker assessments will only be collected during Cycle 1 as of protocol amendment 11."	Update

Section(s)	Change	Rationale
Appendix C	Concerning row PK/ATA, added Cycle 1 only to "See PK/ATA/Biomarker Tables (Appendix D and Appendix E)" as presented in Appendix C.	Update
	Concerning footnote B, added "completion of the safety follow-up period" and "unless otherwise stated".	
	Deleted footnote F, "pregnancy test to be performed 24 weeks (±1 week) after EOT".	
	Deleted footnote S, "response assessments will be collected by BICR for possible future analysis."	
	Added footnote V, added "follow-up will occur every 6 weeks (±1 weeks) 30 days post last treatment for patients on LV only and 90 days for those on pembrolizumab".	
Appendix D	Concerning footnote C, added "Biomarker assessments will only be collected during Cycle 1 as of protocol amendment 11."	Update
Appendix E	Concerning Table 11 footnote C and Table 12 footnote B, added "Biomarker assessments will only be collected during Cycle 1 as of protocol amendment 11."	Update
Appendix G	Deleted the following text, "systemic exposure (at least 6 months after the final dose of study drug; see Section 4.1). the safety follow-up period" and added "the safety follow-up period.	Update
Appendix K	Replaced "in the CRF" with "in the source documents".	Revision

#### LIST OF ABBREVIATIONS

ADC antibody-drug conjugate

AE adverse event

ATA antitherapeutic antibodies CI confidence interval CR complete response CT computed tomography DCR disease control rate DLT dose-limiting toxicity

duration of response ECG electrocardiogram

EOT end of treatment

DOR

**ECOG** 

iCPD confirmed progressive disease based on iRECIST guidelines

Eastern Cooperative Oncology Group

iDOR. duration of response based on iRECIST guidelines iPFS progression-free survival based on iRECIST guidelines iRECIST modified RECIST 1.1 for immune-based therapeutics

iUPD unconfirmed progressive disease based on iRECIST guidelines

MMAE monomethyl auristatin E MRI magnetic resonance imaging

NCI CTCAE National Cancer Institute's Common Terminology Criteria for Adverse Events

ORR objective response rate OS overall survival PD progressive disease

PD-L1 programmed death-ligand 1 PFS progression-free survival

PK pharmacokinetics PP per-protocol PR partial response

RECIST Response Evaluation Criteria in Solid Tumors

SAE serious adverse event SAP statistical analysis plan

SD stable disease

SMC Safety Monitoring Committee TEAE treatment-emergent adverse event

#### 1 INTRODUCTION

This document outlines the statistical methods to be implemented within the scope of Protocol SGNLVA-002, entitled "Single Arm, Open Label Phase 1b/2 Study of SGN-LIV1A in Combination with Pembrolizumab for First-Line Treatment of Patients with Unresectable Locally-Advanced or Metastatic Triple-Negative Breast Cancer". Results of the proposed analyses will become the basis of the clinical study report for this protocol.

The purpose of this plan is to provide specific guidelines from which the analysis will proceed. All planned analyses specified in this document will be performed. Any changes to this plan, in the form of "post hoc" or "data driven" analyses will be identified as such in the final clinical study report. Any changes will either be reflected in amendments to this plan before the database lock or specifically documented in the clinical study report.

#### 2 OBJECTIVES AND ENDPOINTS

Primary Safety Objectives	Corresponding Endpoint

 
Assess the safety and tolerability of the combination of SGN-LIV1A and pembrolizumab in patients with LA/M TNBC
 
Identify the recommended dose of SGN-LIV1A in combination with pembrolizumab in patients with LA/M TNBC
 
	Type, incidence, severity, seriousness, and relatedness of AEs     Laboratory abnormalities     Incidence of dose-limiting toxicity (DLT)
Primary Efficacy Objective	Corresponding Endpoint
Evaluate the confirmed ORR of the combination of SGN-LIV1A and pembrolizumab in patients with LA/M TNBC	Confirmed ORR as determined by the investigator according to RECIST v1.1
Secondary Efficacy Objectives	Corresponding Endpoints
Evaluate the DOR, DCR, PFS, and OS	DOR as determined by RECIST v1.1     DCR as determined by RECIST v1.1     PFS as determined by RECIST v1.1     OS
Exploratory Efficacy Objectives	Corresponding Endpoints

Evaluate the ORR, DOR, DCR, and PFS according to iRECIST	ORR as determined by iRECIST  DOR as determined by iRECIST  DOR as determined by iRECIST  PFS as determined by iRECIST
Pharmacokinetic and Immunogenicity Objectives	Corresponding Endpoints
Assess PK and incidence of antitherapeutic antibodies (ATAs) of SGN-LIV1A	Selected PK parameters for SGN-LIV1A, and MMAE     Incidence of ATAs to SGN-LIV1A
Biomarkers Objectives	Corresponding Endpoints
Evaluate PD-L1 and LIV-1 expression-response relationship     Assess exploratory biomarkers (e.g., in the tumor immune microenvironment or periphery) of study treatmentmediated pharmacodynamic effects	PD-L1 and LIV-1 expression-response relationship following treatment with SGN- LIV1A and pembrolizumab     Relationship between biomarkers in blood and tumor tissue to efficacy, safety, or other biomarker endpoints following treatment with SGN-LIV1A/pembrolizumab

RECIST = Response Evaluation Criteria in Solid Tumors; iRECIST = immune-related RECIST.

#### 3 STUDY DESIGN

This is a single-arm, open-label, multicenter trial designed to assess the safety and efficacy of LV in combination with pembrolizumab for the treatment of LA/M TNBC. Patients will be enrolled into Part A, Part B, Part C, and Part D sequentially. Patients will enroll in Part B Cohort 1 and Part B Cohort 2 sequentially.

In Part A, patients will receive a dose of LV 2.5 mg/kg as an intravenous (IV) infusion over approximately 30 minutes followed by pembrolizumab 200 mg IV over approximately 30 minutes on Day 1 of each 21-day cycle. In consultation with the sponsor, eligible patients already on treatment prior to Amendment 2, may have their maximum weight cap per infusion increased to 100 kg or remain at 80 kg, if they are receiving benefit (complete response [CR], partial response [PR], or stable disease [SD]). Patients receiving >200 mg LV per infusion are required to be administered prophylactic granulocyte-colony stimulating factor (G-CSF). Dosing may be de-escalated based upon the frequency of dose-limiting-toxicities (DLTs) in Cycle 1.

Part B includes 2 expansion cohorts. Part B Cohort 1 will receive the MAD of LV 2.5 mg/kg. Part B Cohort 2 will receive the dose of LV 2.0 mg/kg. Patients will enroll sequentially into

Study SGNLVA-002 Ladiratuzumab vedotin Statistical Analysis Plan Seagen, Inc. - Confidential 01-May-2024 Page 7 of 32 Cohort 1 followed by Cohort 2. Patients receiving >200 mg LV per infusion are required to be administered prophylactic granulocyte-colony stimulating factor (G-CSF).

In Part C, patients will receive LV 1.0 or 1.25 mg/kg on Day 1, Day 8, and Day 15 in every 21-day cycle, not to exceed 200 mg per infusion, in combination with pembrolizumab administered on Day 1 of every cycle. Part C will have dose escalation and expansion cohorts. Dose escalation in Part C will be conducted using the modified toxicity probability interval (mTPI) method (Ji 2010). At least 2 patients will be enrolled in each dose escalation cohort. The safety monitoring committee (SMC) will evaluate the safety of each dose-level cohort and make dose escalation/de-escalation recommendations using the mTPI decision rules. Only 1 dose-escalation cohort will be open at a time.

The dose-expansion cohorts in Part C will assess the efficacy, safety, and tolerability in a larger number of patients. Dose-expansion cohorts may be opened at any dose level that has cleared DLT evaluation. DLT evaluation will only include data from the dose-escalation cohorts; however, the totality of data from all patients at each dose level will be used to determine the recommended q1wk LV dose.

In Part D, patients will receive LV 1.5 mg/kg administered on Day 1 and Day 8 (off Day 15) of every 21-day cycle, not to exceed 200 mg per infusion, in combination with pembrolizumab administered on Day 1 of every cycle. Ongoing, real-time, continuous review of patient safety and serious adverse events (SAEs) will be conducted by the sponsor's Drug Safety Department. Additionally, the independent safety monitoring committee (ISMC) will ensure periodic safety data review throughout the study.

Under Amendment 2 and later, dosing for patients in Parts A and B is based on patient actual body weight, except for patients weighing >100 kg, where dosing will be based on a 100 kg maximum weight per infusion. For patients in Parts C and D, LV dosing is based on the patient's actual body weight but there will be no weight cap per infusion. An individual's dose may be modified based upon treatment-related adverse events (AEs). In all patients, pembrolizumab 200 mg will be administered by IV infusion approximately 60–90 minutes after administration of LV.

Responses will be assessed by computed tomography (CT) scan and/or magnetic resonance imaging (MRI) scan every 6 weeks (±3 days) for the first 12 months after the first dose of LV and pembrolizumab and every 12 weeks (±7 days) thereafter through the end of the safety follow-up period. No additional scans or response assessments are required after the safety follow-up period, however additional scans or response assessments may be performed as part of the patient's standard of care at any time. Objective responses will be confirmed at least 4 weeks after first documentation of response. RECIST v1.1 will be used to score responses for the primary and secondary endpoints, and iRECIST will be used for exploratory endpoints. Investigators will make treatment decisions based on site assessments of scans using iRECIST.

Patients will continue to receive study treatment until disease progression, unacceptable toxicity, investigator decision, consent withdrawal, or study termination by the sponsor.

Study SGNLVA-002 Statistical Analysis Plan 01-May-2024
Ladiratuzumab vedotin Seagen, Inc. - Confidential Page 8 of 32

Pembrolizumab may be administered for a maximum of 35 cycles (approximately 2 years). If LV or pembrolizumab is discontinued, patients may continue to receive the other drug with medical monitor approval. Patients who discontinue study treatment in the absence of disease progression will be followed every 6 weeks for response assessments, physical examinations, and survival until withdrawal of consent, initiation of a new anticancer therapy, death, or study closure, whichever occurs first. After 1 year on study, the frequency of follow-up visits will be reduced to every 12 weeks. All patients, including those with progressive disease (PD), will be followed for survival until the end of the safety follow-up period, death, or study closure, whichever occurs first.

After disease progression or initiation of a new anticancer treatment, survival follow-up will be conducted every 12 weeks (±2 weeks) starting from the last radiographic scan demonstrating disease progression or from initiation of the new anticancer treatment. Survival follow-up will continue until the end of the safety follow-up period, death, or study closure, whichever comes first. Follow-up may be conducted with clinic visits or telephone calls. No further response assessments are required. On a periodic basis, an SMC will monitor the safety of patients participating in the trial. The SMC will be responsible for evaluating the results of safety analyses and will make recommendations to the sponsor. An ongoing, real-time review of patient safety and (SAEs) will also be conducted by the sponsor's Drug Safety Department. In addition, an ISMC composed of physicians who are not involved in this study, as well as sponsor representatives, will periodically review cumulative safety data and provide recommendations to the sponsor. Continuous monitoring of the benefit-risk profile will be conducted and continuation of enrollment to the cohort may be altered depending on the benefit-risk profile.

#### 4 ANALYSIS SETS

This section defines each of the analysis sets that will be utilized.

# 4.1 All Treated Analysis Set

The all treated analysis set will include all patients who receive any amount of SGN-LIV1A or pembrolizumab. The all treated analysis set will be used as the primary dataset for efficacy analysis.

#### 4.2 Safety Analysis Set

The safety analysis set will include all patients who receive any amount of SGN-LIV1A or pembrolizumab. The safety analysis set will be used for all safety and PK analyses. This is also called the all treated patients set for efficacy analyses.

#### 4.3 DLT Evaluable (DE) Analysis Set

The DLT-evaluable (DE) analysis set includes all treated patients in Part A who either (1) experienced a DLT or (2) received at least 75% of intended SGN-LIV1A and pembrolizumab doses and were followed for the full DLT evaluation period. Patients will be replaced for DLT evaluation if, for reasons other than DLT, they are ineligible for DLT evaluation (e.g., pembrolizumab IRR Grade ≥ 3, receipt of prohibited concomitant medication, patient does not meet eligibility criteria), or do not complete the DLT evaluation period.

Study SGNLVA-002 Ladiratuzumab vedotin Statistical Analysis Plan Seagen, Inc. - Confidential 01-May-2024 Page 9 of 32

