The safety analysis set will include patients treated with any amount of LV or pembrolizumab. This is also referred to as the all treated patients set for some efficacy analyses. The DLT-evaluable (DE) analysis set includes all patients in the safety analysis set who either (1) experience a DLT or (2) receive at least 75% of intended LV and pembrolizumab doses and are followed for the full DLT evaluation period (Cycle 1). The DE patient set will be the primary population for Part A, and will be used for the determination of the MAD for Part B. The all treated analysis set includes all enrolled patients who receive any amount of LV or pembrolizumab and will be the primary set for efficacy analysis. The efficacy-evaluable (EE) set includes all patients in the all treated analysis set who have both a baseline and at least 1 evaluable post-baseline disease assessment according to the RECIST v1.1 and iRECIST criteria, or per investigator determination of clinical disease progression.

Exact 95% confidence intervals (CIs) for ORR and DCR will be provided. DOR, PFS, and OS will be analyzed using the Kaplan-Meier method. The primary analyses of efficacy endpoints will be performed for all treated patients analysis set. All safety analyses will be based on the safety analysis set.

Approximately 60 patients total are expected to be enrolled at the MAD assuming that Part A will enroll 12 patients at the MAD and Part B Cohort 1 will enroll approximately 48 patients, at the MAD. Based on the SGNLVA-001 Phase 1 study, it is estimated that about 70% of patients are LIV-1-positive. Thus, approximately 42 LIV-1-positive patients in total will be enrolled at the MAD. Assuming the observed ORR is between 50% and 70%, the widths of 2-sided 95% CIs are summarized below.

Confirmed ORR	Expected width of 95% CI on LIV-1-positive patients (N=42)	Expected width of 95% CI on all patients at the MAD (N=60)
50%	±16%	±13%
60%	±16%	±13%
70%	±15%	±12%

Part B Cohort 2 will enroll approximately 25 patients at 2.0 mg/kg. With the patients in Part A enrolled at 2.0 mg/kg, approximately 30 patients in total will be enrolled at 2.0 mg/kg. Assuming the observed ORR is between 50-70%, the widths of 2-sided 95% CIs are summarized as below.

	Expected width of 95% CI on all patients at 2.0 mg/kg		
Confirmed ORR	(N=30)		
50%	±18%		
60%	±18%		
70%	±16%		

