3.1.5. Dose-Limiting Toxicity

DLTs are only assessed during Part A and dose escalation cohorts in Part C of the study.

The DLT-evaluation period is the first treatment cycle in Part A and Part C dose escalation. Patients who experience a DLT in Cycle 1 should not receive further treatment with LV and pembrolizumab, unless clinical benefit is demonstrated with adequately managed toxicity. Subsequent doses will be defined by the medical monitor in discussion with the site investigator, in the context of the type of AE observed.

The IBs for LV and pembrolizumab individually describe AEs commonly observed relative to either agent, as well as less common serious findings. The respective IBs should be referenced when attributing causality; however, the final decision regarding causality is at the discretion of the investigator.

If any patient enrolled in Part A or Part C dose escalation discontinues the study without DLT during the DLT period, another patient may be enrolled at the same dose level for DLT evaluation. However, the original patient will be included in the safety analysis.

No DLT evaluation will be conducted in Part D, because no DLT was observed with LV 1.5 mg/kg weekly dosing in SGNLVA-001 (see Section 3.2.3.4). Furthermore, pharmacokinetic exposure of LV given 1.5 mg/kg on Days 1 and 8 every 3 weeks will not surpass LV given 1.5 mg/kg weekly.

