3.1.5.2. Dose-Limiting Toxicity in Part C

A DLT in Part C is defined as 1 of the following that is considered related to LV or the combination, and cannot be attributed to pembrolizumab alone:

- Any clinically significant, non-hematologic AE ≥ Grade 3 according to the NCI CTCAE, Version 4.03 (exceptions noted in list below)
- Strade 3 febrile neutropenia
- Grade 4 thrombocytopenia or Grade 3 thrombocytopenia associated with clinically significant bleeding that requires medical intervention
- Grade 4 anemia unrelated to underlying disease
- Discontinuation during Cycle 1 due to treatment-related toxicity
- Inability to receive all 3 doses of LV (Days 1, 8, and 15) due to patient not meeting dosing criteria (see Section 5.2.3.5)
- Prolonged delay (>2 weeks) in initiating Cycle 2 due to treatment-related toxicity
- Grade 5 event (death)

The following events will not be considered a DLT:

- Grade 3 fatigue that improves to ≤ Grade 1 within 3 days with or without medical assessment
- Grade 3 tumor pain that improves to ≤ Grade 1 within 3 days with or without medical assessment

- LV infusion: Grade 3 IRRs that resolve within 1 day with or without medical assessment
- ≥ Grade 3 non-hematological laboratory abnormalities that resolve to ≤ Grade 1 within
 7 days with or without optimal medical management
- Isolated Grade 3 or 4 electrolyte imbalances/abnormalities and Grade 3 elevations in blood glucose not associated with clinical sequelae that are corrected with supplementation/appropriate management within 3 days
- Grade 3 rash that improves to ≤ Grade 2 within 3 days with or without medical treatment
- Grade 3 nausea, diarrhea or vomiting that improves to ≤ Grade 1 within 3 days with or without medical treatment

The following event will not be considered DLT evaluable:

 Pembrolizumab infusion: ≥ Grade 3 IRRs – these patients must be discontinued from pembrolizumab (see Sections 5.6.1.2, 5.6.1.3) and are not evaluable for DLTs.

Patients who do not complete the 21-day DLT evaluation period for reasons other than DLT will not be considered for dose-escalation decisions and/or determination of the MTD. Patients who are considered non-evaluable for dose-escalation decisions and/or MTD and will be replaced at the same dose level.

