#### 5 STATISTICAL CONSIDERATIONS

# 5.1 General Principles

Descriptive statistics (mean, median, standard deviation, minimum, and maximum) will be summarize continuous variables, Frequencies and percentages will be used to summarize categorical variables. The two-sided 95% exact confidence interval using Clopper-Pearson methodology (Clopper 1934) will be calculated for the response rates where applicable (e.g., ORR).

The median survival time will be estimated using the Kaplan-Meier method; the associated 95% confidence interval (CI) will be calculated based on the complementary log-log transformation (Collett 1994).

Unless otherwise specified, data are to be summarized by dose level and overall. DLT analysis will only include patients in Part A and Part C dose finding part.

Any analysis not described in this plan will be considered exploratory, and will be documented in the clinical study report (CSR) as a post hoc analysis or a change to the planned analysis.

To comply with regulatory electronic submission guidelines, listings of all clinical data will be submitted as electronic data sets. To facilitate data review for the study report, only pertinent data listings will be created and attached to the appendix of the CSR. All statistical tables, listings, and figures will be produced using SAS, version 9.3 or more recent. Other statistical software, if used, will be described in the CSR.

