# 6.7 Safety Analyses

The safety analysis set will be used to summarize all safety endpoints.

Adverse events will be coded using Medical Dictionary for Regulatory Activities (MedDRA) Version 19.1 or higher.

Laboratory values will be graded according to the National Cancer Institute (NCI) Common Terminology Criteria for Adverse Events (CTCAE) Version 4.03 or higher.

Concomitant medications will be coded using WHO Drug (version: June 2016 or more recent).

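### The DLT-evaluable set stops at Part A, so the reported Part C DLT incidence defaults to the safety set and counts patients the protocol treats as non-evaluable

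*SAP*

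**What the plan says.** Four sets of statements bear on who counts in a DLT analysis.

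- **The formal set.** SAP 4.3: "The DLT-evaluable (DE) analysis set includes all treated patients in Part A who either" had a DLT, or received at least 75% of the intended doses of both drugs and were followed for the whole evaluation period. Protocol 9.3.1.7 agrees. The protocol synopsis is wider: "The DLT-evaluable (DE) analysis set includes all patients in the safety analysis set who either (1) experience a DLT" or meet the same two conditions. The only use it names is Part A: "The DE patient set will be the primary population for Part A", and the choice of the maximum administered dose for Part B.
- **The scope of the analysis.** SAP 5.1: "DLT analysis will only include patients in Part A and Part C dose finding part". Protocol 3.1.5 matches this: "The DLT-evaluation period is the first treatment cycle in Part A and Part C dose escalation".
- **The default set.** SAP 6.7: "The safety analysis set will be used to summarize all safety endpoints". SAP 4.2 says the same and admits anyone who received any amount of either drug. DLTs are among the summaries listed in SAP 6.7.1. No SAP section names an analysis to be run on the DE set.
- **Evaluability in Part C.** Protocol 3.1.5.2: "Patients who do not complete the 21-day DLT evaluation period for reasons other than DLT will not be considered for dose-escalation decisions" or for determining the MTD, and they are replaced. The same section makes patients with a Grade 3 or higher pembrolizumab infusion reaction non-evaluable. Table 2 is indexed by DLT-evaluable patients, and Appendix M defines the n in its posterior the same way.

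**The concern.** Incidence of DLT is listed as a primary safety endpoint in section 2 of both documents, and Part C is one of the two places where DLTs are assessed. Under SAP 4.3, every Part C escalation patient lies outside the only analysis set built for DLTs. An analyst who follows the SAP literally would take the safety set, restricted to Part C dose finding by SAP 5.1. That set retains patients who left before Day 21 for reasons other than a DLT, and patients with a severe pembrolizumab infusion reaction. Such patients without a DLT add to the denominator and not to the numerator, so the reported rate can only be diluted. The clinical study report could then show a Part C DLT rate on a different n from the one the safety monitoring committee used.

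The wording reads like Part A text that was not extended when Part C was added. That is an inference; neither document gives a reason for leaving Part C out.

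**Working it through.** **1. How many patients are concerned.** Protocol 9.1.3 and SAP 5.2.3 give about 4 to 12 patients in Part C dose escalation over two dose levels. Protocol 3.1.3.1 starts each level with 2 patients and expands to 6 if 1 of 2 has a DLT. Lower end: 2 × 2 = 4. Upper end: 2 × 6 = 12. The stated range is reproduced.

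**2. Size of the DE set.** Part A plans 12 to 24 patients.

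| Definition | Part A | Part C escalation | Total |
|---|---|---|---|
| SAP 4.3 as written | 12–24 | 0 | 12–24 |
| Extended to Part C escalation | 12–24 | 4–12 | 16–36 |

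These are planned enrolments, so they are upper bounds on the evaluable counts.

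**3. Effect on the reported rate.** Let x be the DLTs, n the evaluable patients and k the non-evaluable patients at a dose level. The DE rate is x/n and the safety-set rate is x/(n + k). The documents do not give k, so it is an assumption. With x = 1 and n = 6:

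| k | Safety-set rate |
|---|---|
| 0 | 1/6 = 16.7% |
| 1 | 1/7 = 14.3% |
| 2 | 1/8 = 12.5% |

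One non-evaluable patient lowers the rate by 16.7 − 14.3 = 2.4 percentage points. With none there is no difference.

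**4. Whether escalation decisions could be affected.** At these sizes the denominator can matter in principle: Table 2 prints D for 2/4 and S for 2/5, and D for 3/6 and S for 3/7. But the table's columns and the n in Appendix M are counts of DLT-evaluable patients, and protocol 3.1.5.2 says who is not evaluable. The wording of SAP 4.3 does not enter. The example in step 3 also changes nothing in Table 2, where 1/6 and 1/7 are both printed E. (The printed 1/6 cell does not follow from Appendix M's own rule, which gives unit probability mass of about 2.47 for the stay interval against 2.12 for escalation. That is a separate matter and does not bear on which patients are counted.)

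**5. Whether the Part A criteria carry over to Part C unchanged.** Part A gives one LV dose in Cycle 1; Part C gives three. A patient who misses one LV dose has 2/3 = 67%, below 75%. If LV and pembrolizumab doses are pooled, the figure is 3/4 = 75%, which qualifies. Protocol 3.1.5.2 counts a missed dose as a DLT only when the dosing criteria were not met, and protocol 5.2.5.2 lets doses be skipped for nonclinical reasons with medical monitor approval. A patient who skips one dose that way and completes 21 days without a DLT is not excluded by 3.1.5.2, but is excluded by a 75% rule applied to LV alone. Extending the set without settling this would create a second mismatch with the n used in the mTPI decisions.

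**The case against.** The strongest reply is that nothing is missing where it counts. The protocol body says which Part C patients are non-evaluable, Table 2 and Appendix M use that count for both the escalation decisions and the MTD estimate, and the synopsis definition is not confined to Part A. A reader might infer from SAP 4.3 that Part C had no usable denominator, or that the weekly dose was set on a wrong one. The documents do not support either inference. Escalation ran on the protocol's count, and protocol 3.1.3.2 and SAP section 3 base the recommended weekly dose on all data from the escalation and expansion patients, not on a DE-set rate.

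It can also be said that the SAP does name a set, the safety set, and that the output is a descriptive table of about 4 to 12 patients with no formal testing (SAP 5.7).

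The first reply stands in full for trial conduct. The second does not answer the point. The safety set is what SAP 6.7 prescribes, and for a DLT rate it is the wrong denominator by the protocol's own evaluability rule. The small numbers limit the consequence, but they also make one extra patient visible in the percentage.

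**Conclusion.** The point holds as a defect in the reporting plan. SAP 4.3 and protocol 9.3.1.7 leave Part C out of the DE set while SAP 5.1 plans a Part C DLT analysis, and the SAP's default then supplies a set that keeps patients the protocol treats as non-evaluable. It concerns the reported Part C DLT incidence in about 4 to 12 escalation patients. It does not touch the escalation decisions, the MTD estimate or the basis for the recommended weekly dose.

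The size depends on how many Part C escalation patients were treated but non-evaluable, which the documents do not state. With one such patient beside 6 evaluable patients and 1 DLT, the rate reads 14% instead of 17%; with none, the two sets agree. The correction should be made because a primary safety endpoint is involved and the change is cheap.

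**What to change.** 1. In SAP 4.3, replace the restriction to Part A by *in Part A and in the Part C dose-escalation cohorts*, with Part C expansion patients excluded. Make the same change in protocol 9.3.1.7 at the next amendment. Protocol 9.3 requires an amendment for a change of analysis method only if site conduct changes, so the SAP need not wait.
2. In SAP 6.7 or 6.7.1, state that DLT incidence is summarized on the DE set and not on the safety set.
3. Reconcile the 75%-of-intended-dose criterion with protocol 3.1.5.2 for three weekly LV doses. Say whether it applies to each drug or to both pooled, and how a dose skipped for a reason other than a DLT is counted. The test is that the reported Part C denominator at each dose level equals the n used in the mTPI decisions.

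The cost is a few sentences in the SAP and a matching phrase in the protocol. No new data are needed.
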